10.3.3.1 Primary efficacy variable: primary analysis

The primary analysis of the primary efficacy variable will be performed in FAS.

Randomized subjects without an event of the primary composite endpoint at the time of analysis will be censored at the date of their last visit or date of non-CV death. Subjects without information about the primary composite endpoint after baseline will be censored at Day 1.

In order to evaluate whether finerenone is superior to placebo in prolonging the time to the first event of the primary composite endpoint, the following null hypothesis will be tested using the log-rank test at an overall one-sided significance level of 2.5%, equivalently a two-sided significance level of 5%:

$$H_0: S_{\text{finerenone}}(t) = S_{\text{placebo}}(t) \text{ for all time points } t \geq 0$$

The alternative hypothesis will be:

$$H_1: S_{\text{finerenone}}(t) > S_{\text{placebo}}(t) \text{ for at least one time point } t \geq 0 \text{ and} \\ S_{\text{finerenone}}(t) \geq S_{\text{placebo}}(t) \text{ for all time points } t \geq 0,$$

where $S_{\text{finerenone}}$ denotes the ‘survival’ function of the finerenone treatment group and S_{placebo} denotes the ‘survival’ function of the placebo treatment group. ‘Survival’ means ‘no event of the primary composite endpoint’ in this context.

The following decision rule to test the null hypothesis will be applied:

According to the size of this study it is justified to assume under H_0 a sufficiently close approximation of the log-rank test (47) to the normal distribution. If the z-value from the log-rank test (for the difference $S_{\text{finerenone}} - S_{\text{placebo}}$), stratified by the stratification factors type of albuminuria, region, eGFR category and history of CVD is larger than the critical quantile from the normal distribution ($z_{0.975} = 1.960$), the null hypothesis will be rejected in favor of the alternative hypothesis.

The nominal significance levels and the critical values at the final analysis will be adjusted to account for the interim analysis, see Section 10.5 for more details.

In order to provide a point estimate of the hazard ratio and a corresponding two-sided 95% confidence interval, a stratified Cox proportional regression model will be used.

Kaplan-Meier curves will be provided for the cumulative proportions of events by treatment groups.

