10.3.3.3 Secondary efficacy variables: primary analysis

The primary analysis of the secondary efficacy variables will be analyzed in FAS.

If the null hypothesis of the primary analysis is rejected, the secondary efficacy variables will be tested hierarchically in the order as they are listed in Section 9.4.2, while keeping the two-sided significance level of 5.0%. Otherwise, the testing of the secondary efficacy variables will be performed in an explorative manner only.

The primary analysis of the secondary time-to-event endpoints will be analyzed analogously to the primary analysis of the primary composite endpoint.

An ANCOVA model will be fitted to the logarithmized ratios of UACR at Month 4 to UACR at baseline including the factors treatment group, the stratification factors (type of albuminuria, region, eGFR category, history of CVD) and the logarithmized baseline UACR as covariate. Corresponding two-sided 95% confidence intervals will be computed. This is consistent with the primary analysis of the Phase II Study 16243.

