10.5 Planned interim analyses - *amended*

This section was changed in Amendment 3, see Section 15.1.2.42.

One formal interim analysis is planned when 2/3 of the required total number of primary efficacy endpoint events have been observed. Based on the assumptions from sample size determination the interim analysis will take place between 34 and 38 months after start of study treatment. As an event-driven trial, the actual timing of the interim analysis will depend on the observed event rate, the patient recruitment rate, and length of the recruitment period.

If the interim analysis shows clear and consistent benefit in the finerenone treatment group, the DMC may recommend early study termination. The Haybittle-Peto rule will be used to guide the decision regarding early stopping of the study for success: a reduction of 3 standard deviations in the analysis of the primary efficacy endpoint and the secondary renal composite endpoint at the interim analysis (two-sided p-value < 0.00270).

If the decision will be to stop the study early for success, the final primary analyses, both for the primary and secondary efficacy endpoints, will be performed at an overall two-sided significance level of 0.270%. A group sequential design with a single interim analysis when 2/3 of the information is available with a stopping rule of two-sided $p < 0.00270$ would require a final $p < 0.04968$ to maintain the overall significance level at 5%. Consequently, if the decision will be to continue the study without stopping early for success, the final primary analyses will be performed at a two-sided significance level of 4.968%.

For a lack of efficacy, a non-binding futility approach will be utilized at the time of the planned interim analysis. If the conditional probability of rejecting the null hypothesis for the primary comparison, given the assumed and current event rates, falls to an unacceptably low level (as will be specified in the DMC Charter), the DMC may consider recommending early termination of the study.

The Executive Committee will oversee overall blinded event rates to ensure that they meet protocol projections. If overall event rates are lower than expected, consideration will be given to altering the trial design, such as increasing the sample size or extending the study duration without knowledge of any treatment effect.

11. Data handling and quality assurance

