Assessment Criteria Identification Requirement Document for the phase III DKD studies 16244 and 17530 version 4.0 dated 27 AUG 2019

DMC Charter version 3.1 dated 17 SEP 2019

CEC Charter version 3.0 dated 10 JUN 2019

This SAP describes the statistical analysis of the period from informed consent to randomization, the double-blind placebo-controlled study treatment and post-treatment follow-up phase (expected duration 3 years or more) and the 4-week period up to the post-treatment visit (if applicable). One formal interim analysis is currently planned. An independent data monitoring committee (DMC) will be involved in the review of data for safety and efficacy as described in the DMC Charter. Blinded adjudication of clinical outcomes will be performed by an independent Clinical Event Committee (CEC), as described in the CEC Charter.

Background

Finerenone (BAY 94-8862) is a next-generation, oral, selective, non-steroidal MRA. In animal models, finerenone reduced cardiac and renal hypertrophy, plasma prohormone of brain natriuretic peptide (BNP) and proteinuria more efficiently than in those treated with the steroidal mineralocorticoid receptor antagonist (MRA) eplerenone, when comparing equi-natriuretic doses. Finerenone's tissue distribution pattern in rats was found to differ from the steroidal MRAs, i.e. spironolactone and eplerenone, which showed a higher accumulation of the drug equivalent concentration in kidney than in heart tissue, in contrast to finerenone which was found to be equally distributed in both the kidney and heart tissue. Steroidal MRAs are known to interfere with the steroid hormone receptor, which can cause sexual side effects such as gynecomastia in men. However, finerenone is a non-steroidal and selective MRA in vitro, without any detectable affinity for the related androgen receptor; sexual side effects are therefore not expected to occur with finerenone at therapeutic dose levels. These characteristics may translate to a drug with a positive benefit-risk ratio in patients with DKD.

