4.4 Interim Analyses and Data Monitoring

One formal interim analysis is planned when 2/3 of the required total number of primary efficacy endpoint events have been observed.

If the interim analysis shows clear and consistent benefit in the finerenone treatment group, the DMC may recommend early study termination. The Haybittle-Peto rule will be used to guide the decision regarding early stopping of the study for success: a reduction of 3 standard deviations in the analysis of the primary and the key secondary efficacy endpoint at the interim analysis (two-sided p-value <0.00270).

For a detailed description of the testing procedure, including an adjustment of the significance level for the interim analysis, please see section 4.7.

In case of an early stop of the study for success, the final analysis reported in the CSR will consider all events up to the subjects' respective EoS visits as would have been the case if the study had not stopped early. A sensitivity analysis will take all events up to the interim analysis datacut date into consideration and will be based on the same final clean database as done for the final analysis reported in the CSR (instead of the interim analysis database). For this sensitivity analysis, censoring dates after the datacut date will be reset to the datacut date.

For a lack of efficacy, a non-binding futility approach will be utilized at the time of the planned interim analysis. If the conditional probability of rejecting the null hypothesis for the primary comparison, given the assumed and current event rates, falls to an unacceptably low level (as specified in the DMC Charter), the DMC may consider recommending early termination of the study.

A detailed plan for the routine DMC safety analyses and the interim analysis is covered in the DMC charter, the analysis planned to be provided to the DMC is described in a separate DMC SAP with Tables, Listings and Figures (TLFs) attached to the DMC charter. The DMC will review the data in an unblinded manner, both for the routine safety tables and the interim analysis. There are no predefined stopping conditions for the ongoing safety monitoring of this trial. The statistical analysis for the DMC meetings will be performed by an independent statistical analysis center.

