4.7 Testing procedure and multiplicity adjustment

If the decision will be to stop the study early for success (see section 4.4 for a description of the stopping rules), the final primary analyses, both for the primary and secondary efficacy endpoints, will be performed at a two-sided significance level of 0.270%. Only if both the primary and the key secondary efficacy endpoint achieve this significance level, the corresponding null hypotheses can be rejected and the remaining secondary endpoints will also be tested at a two-sided level of 0.270% according to the following hierarchy:

- Time to all-cause hospitalization
- Time to all-cause mortality
- Change in UACR from baseline to Month 4
- Time to first occurrence of the following renal composite endpoint: onset of kidney failure, a sustained decrease in eGFR of $\geq 57\%$ from baseline over at least 4 weeks or renal death

If the decision will be not to stop the study early for success, the final primary analyses will be performed as follows: A group sequential design with a single interim analysis when 2/3 of the information is available with a stopping rule of two-sided $p < 0.00270$ requires a small adjustment to the final analysis that is slightly lower than $p = 0.05$ to maintain the overall significance level at 5%. A hierarchical testing procedure will be used for the primary and secondary efficacy variables in the order mentioned below with each variable being tested at the adjusted two-sided significance level of 0.04967388, which applies for an information fraction of 2/3.

- Primary CV composite endpoint
- Key renal composite endpoint
- Remaining secondary efficacy endpoints as in the order mentioned above for a stop at the interim analysis

If the testing strategy stops at one point due to a non-significant result, the testing of the remaining secondary efficacy variables will be performed in an explorative manner only.

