- Estimate the hazard at time of loss to follow-up, using a Weibull survival model fitted to the population of subjects who prematurely discontinued study treatment and adjusted for treatment group and stratification factors.
- Inflate the hazard only in the finerenone group by a known factor; assumes non-informative censoring in the control group.
- Impute events to the end of the study 1000 times, calculate the hazard ratios with the stratified Cox model specified in section 6.2.1.1 and combine them using standard multiple imputation combining rules.
- Increase the inflation factor until upper limit of two-sided 95.032612% (or 99.73% at the interim analysis) confidence interval for the hazard ratio crosses 1.0; this will be the “tipping point”.

The tipping point will show how much higher the event risk after drop-out would need to be in the finerenone group so that statistical significance is lost. Since there is no particular reason to assume that the event rate should be higher, a large tipping point will indicate robustness of the study results. Technical details of the model are provided in section 9.1.

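### After an early stop for success, SAP 4.7 makes rejection of the primary null depend on the renal composite also reaching 0.270%, a condition the protocol does not state (minor)

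*SAP*

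**What the plan says.** **SAP 4.7, early-stop branch.** Testing is at two-sided 0.270%, and "Only if both the primary and the key secondary efficacy endpoint achieve this significance level, the corresponding null hypotheses can be rejected". The key secondary is the renal composite with the 40% eGFR component. The plural null hypotheses include the primary one.

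**Protocol 10.3.3.1.** The primary null is rejected if the log-rank z-value, stratified by type of albuminuria, "region, eGFR category and history of CVD is larger than the critical quantile from the normal distribution". The nominal levels and critical values "will be adjusted to account for the interim analysis, see Section 10.5 for more details".

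**Protocol 10.3.3.3.** "If the null hypothesis of the primary analysis is rejected, the secondary efficacy variables will be tested hierarchically". The dependence runs from primary to secondary.

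**Protocol 10.5.** A 3 SD reduction on both the primary endpoint and the renal composite guides the decision to stop. After a stop, the final primary analyses, "both for the primary and secondary efficacy endpoints, will be performed at an overall two-sided significance level of 0.270" per cent. No joint condition for rejection follows.

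**SAP 4.4.** It has the same two-endpoint stopping guide. After an early stop, "the final analysis reported in the CSR will consider all events up to the" subjects' end-of-study visits. An analysis cut at the interim data-cut date, on the same clean database, is a sensitivity analysis.

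**The concern.** If both endpoints have crossed to justify stopping, a joint rejection condition looks redundant. It is not, because the p-values that count are recomputed after the stop on a larger data set. The renal result can cross at the interim and slip back by the end-of-study visits while the primary stays beyond its boundary.

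Suppose the data to end of study give primary p = 0.0005 and renal p = 0.004. Under SAP 4.7 neither null is rejected. Under the protocol's rule the primary null is rejected (0.0005 < 0.0027) and testing stops at the renal composite (0.004 > 0.0027). The documents would then give different answers on the trial's main claim, and the dispute would arise with unblinded results in hand. There is also a second, smaller route. The stopping rule only guides, and the DMC may recommend, so a stop without a joint crossing is not excluded.

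**Working it through.** 1. **Reproduce the plan's levels.** 3 SD gives 2 × (1 − Φ(3)) = 0.0026998, matching 0.00270. For one look at information 2/3, the correlation between interim and final z is √(2/3). Solving P(|Z₁| > 3 or |Z₂| > c) = 0.05 gives c = 1.9628, a two-sided level of 0.049674. This matches 0.04967388 (SAP 4.7) and 0.04968 (Protocol 10.5). The calculation uses the primary endpoint only, so the final level already pays for the primary alone crossing at the interim.

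2. **Allow for the overrun.** Suppose that after a stop the primary alone is tested at 0.270% on the data to end of study. Overall two-sided alpha is then 0.04992 at 5% overrun (information 0.700), 0.04988 at 7.5% (0.717) and 0.04984 at 10% (0.733). All are below 0.05, so removing the joint condition costs no alpha.

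3. **Size of the overrun.** The interim falls at 2/3 × 976 ≈ 651 events. The other 976 − 651 = 325 events are expected over about 10 months (34–38 months for the interim in Protocol 10.5, 44–48 months in total in 10.4), or 32.5 a month. The 4-week window for end-of-study visits gives about 30 events, and 30/651 = 4.6%. Two months in all gives 65/651 = 10%. The range used is therefore 5–10%.

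4. **Chance that the primary crosses.** The interim drift is (√d / 2) × |ln HR|. The hazard ratio at which 976 events give 90% power is exp(−2 × (1.960 + 1.2816)/√976) = 0.8126. With d = 651, the drift is 12.757 × 0.2075 = 2.647, and Φ(2.647 − 3) = 0.36. At HR 0.80 it is 12.757 × 0.2231 = 2.847, giving 0.44.

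5. **Renal slippage after a joint stop.** The documents give no renal event count, renal effect or correlation, so these are assumed. The grid has 54 scenarios: primary HR 0.75, 0.80, 0.8126; renal HR 0.70, 0.75, 0.80; 300, 350, 400 renal events at the interim; 5% or 10% overrun; correlation 0.3. It uses simulated bivariate normal statistics, independent increments after the interim, and a boundary of z = 3.

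| Quantity | Range | Median |
|---|---|---|
| Both endpoints cross at the interim | 7.9–56.9% of trials | – |
| Primary holds, renal slips, given a joint stop | 1.5–12.7% | 5.3% |
| Same, renal HR 0.70–0.75 only | 1.5–7.8% | 3.8% |
| Same event, as a share of all trials | 0.4–2.0% | 1.0% |
| Primary itself slips, given a joint stop | 1.2–6.8% | – |

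Correlation 0.1 or 0.5 moves the medians to 5.8% or 5.0% of stopped trials and 0.9% or 1.1% of all trials. The upper end of the range needs renal HR 0.80, where both endpoints cross in only 8–19% of trials. The fix does not address the last row of the table, and should not.

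**The case against.** The strongest reply is that the protocol is silent rather than opposed. Protocol 10.5 makes early stopping for success a joint matter and sets one level for the primary and secondary endpoints together. It does not say how the endpoints are tested against each other after a stop. Protocol 10.1 leaves further detail to the SAP, and SAP 7.2 records section 4.7 as the full specification of the testing procedure. Carrying the joint criterion into the rejection rule can be read as filling a gap. This stands in part: the condition may be deliberate. It does not settle the matter, because 10.3.3.1 gives a complete decision rule for the primary and sends only levels and critical values to 10.5.

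Second, SAP 4.4 keeps the data-cut analysis, so the result before any drift would still be reported. That is a real mitigation. As a sensitivity analysis, however, it does not restore the formal claim.

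Third, the branch may not be reached. If the trial runs to its final analysis, the sentence has no effect. The SAP introduction still says "One formal interim analysis is currently planned", which is weak evidence either way, and the documents do not say whether the interim had taken place.

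A reader might also see an inconsistency inside the SAP, because the tipping-point analysis in 6.2.1.2 looks only at whether the primary's own interval ("or 99.73% at the interim analysis) confidence interval for the hazard ratio crosses 1.0") loses significance. That inference fails. Under a joint rule, the primary missing 0.270% is enough to lose the claim, so the analysis fits either rule. Nor do the plain hierarchy in the no-stop branch of SAP 4.7, or SAP 6.2.1.1 (which defers to 4.7), contradict the joint condition.

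**Conclusion.** The point holds, as a minor one limited to the early-stop branch. SAP 4.7 adds a condition for rejecting the primary null that Protocol 10.3.3.1, 10.3.3.3 and 10.5 do not contain, and the reported analysis to end of study gives that condition a way to matter.

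Two stronger readings are not supported. The protocol does not forbid a joint rule; it does not state one. And the SAP rule does not inflate type I error: it is stricter, and the risk is losing a valid claim.

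The size is about 1.5–12.7% of stopped trials (median 5.3%) and about 1% of all trials. It depends on the assumed renal event count, renal hazard ratio, correlation and overrun. The difference between the texts and the alpha result do not depend on the renal assumptions.

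**What to change.** In the early-stop branch of SAP 4.7, replace the joint condition with an ordered test: the primary alone at two-sided 0.270%; if rejected, the key renal composite at 0.270%; then the remaining secondaries in the listed order. Keep the joint crossing in SAP 4.4 as the guide to stopping only. The conditions for claiming the renal composite and every later secondary are unchanged, since each already requires the primary to reach 0.270%.

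If the joint rejection rule is intended, keep it and state it in Protocol 10.3.3.1, 10.3.3.3 and 10.5, so that both documents give the same rule.

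The cost is one sentence in the SAP, or one in each of three protocol sections. Neither route needs new data, patients, analyses or alpha. The change should be made before unblinded results are available to those who decide it.

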4.8 Considerations with regard to the COVID-19 pandemic

As the last year of the study conduct period overlaps with the global COVID-19 pandemic declared by the WHO on 11 MAR 2020, some subjects are expected to be affected by the COVID-19 pandemic either directly (i.e. because of an infection) or indirectly (e.g. treatment interruptions or missed measurements/endpoints because a subject did not go to the site out of fear of infection, due to travel ban or because the site was closed). Randomization had been completed for almost one year (January 2019) prior to the COVID-19 pandemic, so randomized subjects are only potentially affected at a late stage of their observation period. The impact of the pandemic will be assessed by several analyses described throughout Sections 6.1 (Population characteristics), 6.2.4 (Supportive efficacy analyses related to the COVID-19 pandemic) and 6.4.1 (Adverse events).

To account for the different ways in which subjects might be impacted by the pandemic, two (overlapping) groups of subjects are identified:

- subjects with COVID-19 adverse event,
- subjects affected by any COVID-19 pandemic-related study disruption (adverse event, missed visits, study drug interruptions, protocol deviations, etc.).

Thus when analyses for subjects affected by the COVID-19 pandemic are mentioned in the following, both these groups will be considered separately unless specified otherwise.

The reasons for specific intercurrent events (temporary or permanent treatment discontinuations) and missing data (missed visits or missed eGFR re-tests) related to the COVID-19 pandemic will be differentiated as follows: subject decision, physician decision and logistical reason.

In terms of the onset date of the COVID-19 pandemic (used as cut-off date in supportive efficacy analyses, see Section 6.2.4), four different versions will be evaluated to differentiate the broad impact vs. actual individual impact with distinction between any impact vs. direct impact (through an infection):

- *Country-specific COVID-19 onset date* (primary choice): date of first COVID-19 patient reported by the WHO per country [13]
- *Global COVID-19 onset date*: 11 MAR 2020 (the date when the WHO declared the COVID-19 pandemic), except for China: 31 DEC 2019 (the date when health authorities in China reported to the WHO China Country Office)
- *Individual COVID-19 impact onset date*: earliest date when the subject was affected by any COVID-19 pandemic-related study disruption
- *Individual COVID-19 adverse event onset date*: earliest date when the subject was affected by a COVID-19 adverse event

5. Analysis Sets

Subjects will be excluded from all below-mentioned analysis sets if they are related to critical GCP violations.

